ANCOVA	analysis of covariance
APACHE II	Acute Physiology and Chronic Health Evaluation II
ATP	according to protocol
BMI	body mass index
CHF	Congestive heart failure
COPD	Chronic obstructive pulmonary disease
CLSI	Clinical and Laboratory Standards Institute
CPIS	Clinical pulmonary infection score
CRP	C reactive protein
CSR	clinical study report
DBL	database lock
DMC	Data Monitoring Committee
EAC	endpoint adjudication committee
eCRF	electronic case report form
ECG	electrocardiogram
EU	European Union
GOLD	Global initiative for chronic Obstructive Lung Disease classification
HADS	hospital anxiety and depression scale
ICU	intensive care unit
Ig	immunoglobulin
IM	immunogenicity
ITT	intent-to-treat
IV	intravenous
IXRS	interactive voice/web response system
LLOQ	lower limit of quantification
MedDRA	Medical Dictionary for Regulatory Activities
MIC	Minimum Inhibitory Concentration
NCI CTCAE	National Cancer Institute Common Terminology Criteria for Adverse Events

Abbreviation or Specialized Term	Definition
NYHA	New York Heart Association functional classification
P aeruginosa	Pseudomonas aeruginosa
P _a O ₂ /F _i O ₂	ratio of partial pressure arterial oxygen and fraction of inspired oxygen
PT	preferred term
PK	pharmacokinetics
SAE	serious adverse event
SAP	statistical analysis plan
SC	subcutaneous
SID	subject identification number
SOC	system organ class
SOFA	sequential organ failure assessment
SPP	statistical programming plan
SSR	Sample size re-estimation
TFL	tables, figures and listings
VAP	Ventilator-associated pneumonia
WBC	white blood cell

1 INTRODUCTION

This document describes the statistical analysis for protocol D5470C00004, a proof-of-concept study to evaluate the efficacy and safety of MEDI3902 in mechanically ventilated patients for the prevention of nosocomial pneumonia caused by *Pseudomonas aeruginosa*.

A separate Statistical Programming Plan (SPP) will be created to give details for the planned Tables, Figures and Listings for this study.

2 STUDY OVERVIEW

2.1 Study Objectives

2.1.1 Primary Study Objective(s)

- 1 To evaluate the effect of MEDI3902 in reducing the incidence of nosocomial pneumonia caused by *P aeruginosa*
- 2 To evaluate the safety of a single IV dose of MEDI3902 in mechanically ventilated patients

2.1.2 Secondary Study Objectives

- 1 To evaluate the serum pharmacokinetics (PK) of MEDI3902
- 2 To evaluate the serum ADA responses to MEDI3902

Redacted

[Redacted text block containing multiple lines of obscured content]

Redacted

[figure not shown]
2.2 Study Design

This is a Phase 2, randomized, double-blind, placebo-controlled, single-dose, dose-ranging, proof-of-concept study evaluating 2 dosage levels of MEDI3902 in mechanically ventilated patients in the intensive care unit (ICU) who are at high risk for *P aeruginosa* infections and who are currently free of *P aeruginosa*-related disease but are colonised with *P aeruginosa* in the lower respiratory tract. At study start, approximately 429 subjects were to be enrolled and dosed at approximately 120 sites primarily in Europe. Subjects were to be randomly assigned in a 1:1:1 ratio to receive a single IV dose of Redacted or Redacted mg MEDI3902, or placebo. However, based on data from a separate study in a similar population with another monoclonal antibody, data from a PK study in mice (see Protocol Section 3.2.1) and from simulation results using data from the Phase 1 study (Study D5470C00002), a single dose of Redacted mg MEDI3902 is not expected to maintain the target level of Redacted µg/mL for 21 days. Therefore, enrolment in the Redacted mg MEDI3902 group will be discontinued. Approximately 286 subjects will be randomized in a 1:1 ratio to one of 2 treatment groups, Redacted mg MEDI3902 or placebo (N = 143 for each treatment group).

A PK interim analysis will be performed after at least 10 subjects in each of the Redacted mg MEDI3902 and placebo groups are followed through 21 days postdose. The interim PK analysis will allow the determination of serum PK profile of MEDI3902 in mechanically ventilated subjects. Enrolment will continue in both the Redacted mg MEDI3902 and placebo groups while the PK interim analysis is conducted. If the mean serum concentration of MEDI3902 on Day 22 in the Redacted mg MEDI3902 dose group is lower than the target concentration of Redacted µg/mL, a dose adjustment to Redacted mg MEDI3902 will be considered. An independent DMC will be responsible for recommending dose adjustment.

In case of a dose adjustment from Redacted mg to Redacted mg MEDI3902, approximately 143 subjects will be randomized to receive the Redacted mg MEDI3902 dose to maintain 1:1 ratio with the placebo group. Subjects who have been enrolled and randomized in the Redacted mg and Redacted mg MEDI3902 groups will be followed until the end of the study period (Day 50).

Randomization will be stratified by country and by whether subjects received anti-*P aeruginosa* antibiotic treatment (no antibiotics use, duration of ≤ 72 hours, duration > 72 hours) within the 96 hours prior to randomization. Subjects will be followed through Day 50.

Legend

↓ MEDI3902/placebo administration

↓ Post-dose follow-up

Redacted; IV = intravenous; N = number of subjects; PK = pharmacokinetics

- (a) In case of a dose adjustment from Red mg to Red mg MEDI3902, approximately 143 subjects will be randomized to receive the Red mg MEDI3902 dose to maintain 1:1 ratio with the placebo group. Subjects who have been enrolled in the Red mg and Red mg MEDI3902 groups will be followed until the end of the study period (Day 50).

Note: This study flow diagram was revised based on the change in the study design and illustrates how approximately 286 colonised subjects will be randomized in a 1:1 ratio to one of the two treatment groups Reda mg MEDI3902 (or Red mg in case of dose adjustment; N = 143) or placebo (N = 143). Efficacy will be assessed through 21 days postdose (Day 22); safety, PK and ADA will be assessed through 49 days postdose (Day 50). The sample size may be modified after approximately 50% of the subjects are enrolled and followed through 21 days postdose based on blinded assessment of the event rate and/or attrition rate in the overall population.

2.3 Treatment Assignment and Blinding

An interactive web response system (IWRS) will be used for randomization to a treatment group and assignment of blinded investigational product kit number. Subjects will be randomized at a 1:1 ratio to receive either MEDI3902 Reda mg or placebo (or in case of dose adjustment Reda mg MEDI3902). Randomization will be stratified by country and by whether subjects received anti-*P. aeruginosa* antibiotic treatment (no antibiotics use, duration of ≤ 72 hours, duration of > 72 hours) within the 96 hours prior to randomization.

2.4 Sample Size

Approximately 286 colonised subjects will be enrolled and randomly assigned (1:1 ratio) to Reda mg MEDI3902 (n = 143) or placebo (n = 143). In case of a dose adjustment from Reda mg to Reda mg MEDI3902, approximately 143 subjects will be randomized to receive the Reda mg MEDI3902 dose to maintain 1:1 ratio with the placebo group. Subjects who have

been enrolled and randomized in the **Re** mg and **Reda** mg MEDI3902 groups will be followed until the end of the study period (Day 50).

Key assumptions used for sample size/power calculations: placebo group *P aeruginosa* pneumonia incidence 20%, relative reduction 50%, at least 80% power, 20% adjustment for attrition. Relative reduction of 50% was recommended to Sponsor as a clinically meaningful effect by experts in critical care, pulmonary medicine, and infectious diseases.

Statistical methods: power calculations are based on Poisson regression with robust variance comparing MEDI3902 versus placebo, 2-sided, with $\alpha = 0.2$.

2.4.1 Blinded Sample Size Re-estimation

Redacted

[Redacted]

[Redacted]

[Redacted]

[Redacted]

[Redacted]

- [Redacted]

- [Redacted]

- [Redacted]

- [Redacted]

- [Redacted]

- [Redacted]

- [Redacted]

- [Redacted]

- [Redacted]

- [Redacted]

- [Redacted]

- [Redacted]

- [Redacted]

- [Redacted]

- [Redacted]

- [Redacted]

- [Redacted]

- [Redacted]

Redacted

[Redacted]

[Redacted]

3 STATISTICAL METHODS

3.1 General Considerations

Data will be provided in data listings sorted by treatment group and subject identification number (SID). Tabular summaries will be presented by treatment group. Categorical data will be summarized by the number and percentage of subjects in each category. Continuous variables will be summarized by descriptive statistics, including mean, standard deviation, median, minimum, and maximum. No multiplicity adjustments will be made to any of the analyses. In general, unless stated otherwise, baseline will be defined as the last value prior to dosing.

The key efficacy analyses will be based on Reda mg MEDI3902 and placebo subjects. Subjects who received Red mg MEDI3902 will be summarized descriptively for both efficacy and safety.

All statistical tests will be 2-sided at an alpha = 0.2 significance level unless stated otherwise.

Data analyses will be conducted using the SAS[®] System Version 9.3 or higher (SAS Institute Inc., Cary, NC) in a UNIX platform.

3.2 Analysis Populations

The analysis populations are defined in Table 1.

Table 1 Analysis Populations

Population	Description
ITT	All subjects who are randomized. Subjects will be analyzed according to their randomized treatment group.
modified ITT (mITT) population	Subjects who receive any study investigational product will be included in the mITT population and subjects will be analyzed according to their randomized treatment group.
As-Treated population	Subjects who receive any study investigational product will be included in the As Treated population and subjects will be analyzed according to the treatment they actually receive.

ITT = intent-to-treat

3.3 Strata

Many analyses are presented by, or adjusted for, the stratification factor ‘anti-*P aeruginosa* antibiotic treatment (no antibiotics use, duration of ≤ 72 hours, duration of > 72 hours) within the 96 hours prior to randomization’. For subjects who were assigned to an incorrect stratum at randomization, the stratum recorded on the electronic case report form (eCRF) will differ from the stratum recorded for the subject in the IXRS database. Unless stated otherwise, the stratum on the eCRF will be used.

3.4 Study Subjects

3.4.1 Subject Disposition and Completion Status

Subject disposition will summarise the total number of subjects screened and the reasons for screen failure: did not meet inclusion/exclusion criteria, lost to follow-up, withdrawal of consent, and other. The summary will also include the number of subjects randomized, the number of subjects randomized and dosed, and the number of subjects randomized and not dosed and the reason the subject was not dosed: AE, or other. The summary of subject status at the end of the study will include the number and percentage of subjects who completed the study (i.e. completed the Day 50 follow-up visit) and the number and percentage of subjects who discontinued the study due to reasons such as: lost to follow-up, withdrawal of consent, death, or other. This summary will be presented by treatment group, for MEDI3902 total, and for all subjects combined. The denominators for this summary will include all subjects who were randomized and dosed.

A further summary showing eligibility of subjects for each of the study analysis populations will be provided. The denominator for this summary will include all subjects who were randomized into the study.

3.4.2 Demographics and Baseline Characteristics

Enrolment will be summarized by site and by country and site for each treatment group, for MEDI3902 total, and for all subjects combined. The total number of subjects randomized into each treatment group will be used as the denominator.

Enrolment will also be summarized by country and pre-dose anti-*P aeruginosa* antibiotic stratum for each treatment group, for MEDI3902 total, and for all subjects combined. The total number of subjects in the mITT population will be used as the denominator. The number of mis-stratified subjects (i.e. the true pre-dose anti-*P aeruginosa* antibiotic recorded on the eCRF does not match the IXRS database) will be noted. This will be done for each country as well as for all countries combined.

Demographic will be summarized in the intent-to-treat (ITT) and the modified intent-to-treat (mITT) population by treatment group, for MEDI3902 total, and for all subjects combined. Subjects will be excluded from the summary (e.g. means and percentages) of an individual parameter if data are missing.

Demographic information related to gender, age (years), age category (< 65 years, ≥ 65 years), ethnicity, race, weight (kg), height (cm), body mass index (BMI) (kg/m²), and BMI category (≤ 30, > 30) will be summarised. Actual weight will be recorded when available. If actual weight is not available, estimated weight will be recorded. BMI will be calculated based on the weight (actual or estimated) provided.

Baseline characteristics (i.e. clinical severity scores, comorbidities, risk factors within the last 3 months prior to randomization, and ventilator associated pneumonia (VAP) prevention) will be summarized for subjects in the mITT population by treatment group, for MEDI3902 total, and for all subjects combined. Subjects will be excluded from the summary (e.g. means and percentages) of an individual parameter if data are missing.

Summaries of clinical severity scores at baseline (defined as the last assessment prior to dosing) will include Acute Physiology and Chronic Health Evaluation II (APACHE II), Sequential Organ Failure Assessment (SOFA), and Clinical Pulmonary Infection Score (CPIS). For CPIS and SOFA, the total scores are sums of the individual score components, respectively. For any component which is 'Not Done', a total score cannot be calculated. For APACHE-II, the total score is the sum of A+B+C, where (A) = Acute Physiology Score (APS) Points, (B) = Age points, and (C) = Chronic Health Points. The calculation for APS Points (A) is below:

- Total APS Points = [Temperature + Mean Arterial Pressure + Heart Rate + Respiratory Rate + [((A-aDO₂ or PaO₂) + Arterial pH) or Serum HCO₃] + Serum Sodium + Serum potassium + Serum creatinine + Hematocrit + WBC + Glasgow Coma Scale Score]

- If Arterial Blood Gas (ABGs) are not performed (ie, no result for Oxygenation (both AaDo₂ and PaO₂ are ‘Not Done’) and Arterial pH is ‘Not Done’), use the serum HCO₃ value in the APS Score calculation. If Oxygenation and Arterial pH are both ‘Not Done’ and serum HCO₃ is also ‘Not Done’, APS points cannot be calculated and therefore, APACHE-II cannot be calculated.

The following comorbidities will be summarized:

- Chronic obstructive pulmonary disease (COPD)
- Congestive heart failure (CHF)
- Severe COPD (GOLD Stage III/IV) without advanced CHF
- Advanced CHF (NYHA Class III/IV or ACC-AHA Stage C/D) without severe COPD
- Both severe COPD and advanced CHF
- Any other comorbidity:
 - Coronary Artery Disease (including Myocardial Infarction)
 - Angina (chest pain/discomfort)
 - History of angioplasty
 - Peripheral vascular disease
 - Cerebrovascular disease
 - Hypertension
 - Chronic liver disease
 - Diabetes
 - Pulmonary artery hypertension
 - Renal insufficiency or renal failure
 - Thoracic malignancy or any malignancies
 - Known immunodeficiency

The Minimum Inhibitory Concentration (MIC) Clinical and Laboratory Standards Institute (CLSI) susceptibility profile of *P aeruginosa* strain in tracheal aspirate at baseline will summarize multidrug-resistant (MDR), extensively drug-resistant (XDR), pandrug-resistant (PDR), and non-MDR. Baseline is defined as the last value prior to dosing.

Risk factors history within 3 months prior to randomization will summarise supplemental oxygen use prior to hospital admission, history of previous staph infections or colonization, history of *P aeruginosa* infections or colonization, history of other infection(s) (which required either oral or IV antibiotic) (yes/no), antibiotic usage (yes/no), hospitalized (yes/no), and resided in long term care prior to hospitalization (yes/no).

VAP prevention measures at baseline will summarise elevation of the head of the bed (yes/no), daily ‘sedation vacations’ and assessment of readiness to extubate (yes/no), peptic

ulcer disease prophylaxis (yes/no), deep venous thrombosis prophylaxis (yes/no), daily oral care with chlorhexidine (yes/no), and all 5 measures used (yes/no).

3.4.3 Study Drug Exposure

The amount of investigational product infused will be summarized by milligrams (mg) for subjects in the 'As-Treated' population by treatment group. The actual total amount of investigational product infused will be calculated based on the treatment group to which the subject was assigned and the dose intensity. If the entire dose was administered, the dose intensity will be assumed to be 100%. If the entire dose was not administered, dose intensity will be calculated as a percentage of actual volume of investigational product given (mL) against the volume that was intended to be administered (ie, 100 mL). The actual total amount of investigational product infused (mg) = dose intensity * treatment group (mg). For this study, the IV treatment group is either **Redacted** mg, or **Redacted** mg or **Redacted** mg **Redacted** **Redacted**

An additional table will summarise the number of infusion interruptions and the median length of interruptions (minutes).

3.5 Efficacy Analyses

3.5.1 Primary Efficacy Endpoint and Analyses

3.5.1.1 Primary Efficacy Endpoint

The primary endpoint is the incidence of nosocomial pneumonia caused by *P aeruginosa* (as determined by the Endpoint Adjudication Committee [EAC]) through 21 days postdose. For subjects with multiple *P aeruginosa* pneumonia events, only the first occurrence will be used in the primary analysis. Subjects with mixed culture results, which include *P aeruginosa*, will be counted towards the primary endpoint.

The analysis of *P aeruginosa* pneumonia rates will be based on the protocol-specified definition as described in the Protocol (Section 4.3.1.4). The EAC will determine the onset and resolution date and time of the *P aeruginosa* pneumonia event. In general, the onset will be the date and time when the first criteria were met (ie, radiographic, clinical, or microbiologic). For clinical criteria, for example, if a subject starts with fever, then the next day develops purulent secretions and meets the radiographic and microbiologic criteria later, the date of onset would typically be the date of the fever, subject to EAC review.

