## 4.3.1.2 Microbiology

The schedule of follow-up procedures is shown in Table 4.2.2-1. Additional procedures for subjects who have suspected or confirmed pneumonia, tracheobronchitis or bacteremia are shown in Table 4.2.2-2 and are described below.

All subjects with onset of suspected or confirmed pneumonia, tracheobronchitis or bacteremia through Day 29 (irrespective of anatomical location) of the follow-up period, will have blood and respiratory specimens collected at onset (Day 1) of the suspected or confirmed infection. The first set of blood and respiratory specimens will be collected on Day 1 of infection before the start of any new antibiotic therapy and will continue on Days 2 and 3 of infection. Blood samples will be sent for culture and respiratory samples will be sent for Gram stain and culture.

Only subjects who are positive for *P aeruginosa* bacteremia, *P aeruginosa* pneumonia or *P aeruginosa* tracheobronchitis will have additional samples taken for microbiological assessment after Day 3 of infection. For subjects who are positive for *P aeruginosa* bacteremia, blood samples will continue to be collected every other day beginning at Day 4 of infection until blood culture is negative for *P aeruginosa*. For subjects who are positive for *P aeruginosa* pneumonia or *P aeruginosa* tracheobronchitis, respiratory samples will continue to be collected as clinically indicated until clinical resolution.

For respiratory specimens, tracheal aspirate will be collected if the subject is intubated. If the subject is not intubated at onset of suspected or confirmed pneumonia, tracheobronchitis or

bacteremia or is extubated thereafter, expectorated sputum samples will be collected (unless bronchoscopy was performed for clinical management and a bronchoalveolar lavage [BAL] or protected-specimen brush [PSB] sample is available).

If pleural fluid aspirate or lung tissue is obtained as part of the subject's necessary clinical management, the sample should also be sent for Gram stain and culture.

Qualitative respiratory culture results will be recorded by all study sites. Quantitative and semi-quantitative respiratory culture results will be recorded by study sites when available.

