## 4.3.1.4 Definition of *P aeruginosa* Pneumonia

## P aeruginosa Pneumonia Criteria for Subjects Who Are Mechanically Ventilated

A mechanically ventilated subject is intubated with an endotracheal or nasotracheal tube and receiving positive pressure ventilation support, or is not intubated with an endotracheal or nasotracheal tube, but requires  $\geq 8$  hours of positive pressure ventilation (eg, subjects with tracheostomy, continuous positive airway pressure, etc) within the past 24 hours.

Subjects should demonstrate the following new onset of symptoms/signs deemed not due to any overt noninfectious causes. All 3 criteria (ie, radiographic, clinical, AND microbiologic) must be met in order to meet the *P aeruginosa* pneumonia endpoint.

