#### 1. Radiographic criteria:

a. New or worsening infiltrate consistent with pneumonia on chest x-ray obtained within 24 hours of the event (diagnosed by a qualified radiologist)

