#### AND

2. Clinical criteria: At least 2 of the following minor or 1 major respiratory sign or symptom of new onset:

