#### AND

- 3. **Microbiologic confirmation** (obtained within 24 hours of onset of the event): At least 1 of the following:
  - a. Respiratory specimen positive for *P aeruginosa* by culture includes a specimen of respiratory secretion obtained by endotracheal aspiration or by bronchoscopy with BAL or PSB sampling in intubated subjects. In subjects who are not intubated but meet the protocol definition of mechanical ventilation, a specimen of expectorated sputum would be acceptable.
  - b. Blood culture positive for *P aeruginosa* (and no apparent primary source of infection outside the lung)
  - c. Pleural fluid aspirate or lung tissue culture positive for *P aeruginosa* during episode of pneumonia (only if obtained as part of the subject's necessary clinical management)

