#### AND

- 3. **Microbiologic confirmation** (obtained within 72 hours of onset of the event): At least 1 of the following:
  - a. Respiratory specimen positive for *P aeruginosa* by culture. Includes either expectorated sputum or (only if obtained as part of the subject's necessary clinical management) a specimen of respiratory secretions obtained by bronchoscopy with BAL or PSB sampling
  - b. Blood culture positive for *P aeruginosa* (and no other apparent primary source of infection outside the lung)
  - c. Pleural fluid aspirate or lung tissue culture positive for *P aeruginosa* (only if obtained as part of the subject's necessary clinical management)

During study execution, a blinded independent endpoint adjudication committee will review the data for adjudication of efficacy endpoints.

In addition to the primary endpoint, the Phase 2 study includes key secondary and exploratory endpoints, which will be used to guide Phase 3 development for MEDI3902.

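### Does dating pneumonia onset at the first sign push ventilated events outside the protocol's 24-hour culture window?

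*SAP*

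**What the plan says.** SAP 3.5.1.1 counts primary events by the definition in protocol 4.3.1.4 and has the Endpoint Adjudication Committee (EAC) fix the date and time of onset. The general rule is: "In general, the onset will be the date and time when the first criteria were met (ie, radiographic, clinical, or microbiologic". In the worked example a subject has fever, then purulent secretions the next day. If that subject "meets the radiographic and microbiologic criteria later, the date of onset would typically be the date of the fever". The rule is worded as general, the example as typical, and the result is left to EAC review.

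Protocol 4.3.1.4 requires radiographic, clinical and microbiologic criteria together, with these timing terms:

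- Culture, ventilated subjects: "obtained within 24 hours of onset of the event".
- Culture, subjects no longer ventilated: "obtained within 72 hours of onset of the event".
- X-ray, both groups: "on chest x-ray obtained within 24 hours of the event".
- Clinical criterion: two minor signs or one "major respiratory sign or symptom of new onset". Fever belongs to a single minor item.
- Lead-in for ventilated subjects: "Subjects should demonstrate the following new onset of symptoms/signs deemed not due to any overt noninfectious causes".

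For sampling, protocol 4.3.1.2 says that subjects with suspected or confirmed infection through Day 29 "will have blood and respiratory specimens collected at onset (Day 1) of the suspected or confirmed infection", with further sets on infection Days 2 and 3. Table 4.2.2-2 has the same schedule and labels its first column as Day 1 and onset.

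**The concern.** The SAP and the protocol use the same word, onset, and neither says whether the SAP's date starts the protocol's clocks. If it does, the SAP's own illustration can fail the definition that the SAP adopts: the clock starts at a lone fever, and the culture may come more than 24 hours later.

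Three further points add to the unease.

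- On the day of the fever no full criterion has been met, because one minor sign is not enough. The rule and the example therefore do not quite agree.
- The rule lists microbiologic among the criteria that can come first. Every subject is colonised at entry, and intubated subjects have routine aspirates on Days 2 and 4, so a culture showing only colonisation might seem able to set onset.
- The onset date also bears on the 21-day cut-off. With fever on Day 22 and secretions on Day 23, the event is in under the example, but out if the full clinical criterion sets onset.

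At stake would be primary events lost or classified inconsistently.

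**Working it through.** The plan states no figure on this point, so there is none to reproduce. The check is clock arithmetic on the SAP's example, followed by a reading of the texts together.

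**1. Gap between fever and secretions.** Let fever occur at clock hour U1 on one day and secretions at clock hour U2 on the next. The gap is G = 24 + U2 − U1 hours, which is more than 0 and less than 48.

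**2. Chance of missing 24 hours if fever prompts no specimen.** Let the first specimen come d hours after the secretions. It is late when G + d > 24, that is, when U1 − U2 < d. Assume that U1 and U2 are independent and uniform over 0 to 24 hours (the documents do not give this). Then, for d from 0 to 24:

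P(late) = 1 − (1 − d/24)² / 2

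| d (hours) | Calculation | P(late) |
|---|---|---|
| 0 | 1 − 1/2 | 50.0% |
| 6 | 1 − 0.75²/2 = 1 − 0.28125 | 71.9% |
| 12 | 1 − 0.5²/2 = 1 − 0.125 | 87.5% |
| 24 | 1 − 0 | 100% |

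For subjects no longer ventilated, G + d > 72 requires d > 24, because G is below 48. A specimen taken within a day of the secretions is always in time.

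**3. If fever does prompt a specimen.** The delay from the SAP's onset is then about zero and the 24-hour window is met. Protocol 4.3.1.2 asks for specimens at onset of suspected infection and before any new antibiotic, and Table 4.2.2-1 has inpatients monitored daily for signs of pneumonia. Where fever raises suspicion, the sampling anchor and the SAP's onset coincide. The percentages above describe only the other branch, and the documents do not say how often it occurs.

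**4. Criterion met versus specimen obtained.** The protocol's window concerns when the confirmation is obtained. The SAP's example concerns when the criterion is met. A specimen drawn at the fever and reported positive two days later is consistent with both.

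**5. What the SAP sentence dates.** It has the EAC determine onset and resolution of the pneumonia event. A natural reading is that the definition is applied first and the qualifying event is dated afterwards. On that reading the SAP date does not start the culture clock.

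**6. Colonisation.** The definition already requires new signs, and the culture must lie within the stated window of the event's onset. A positive aspirate with no new signs is not an event under 4.3.1.4 and cannot be dated as one. The screening culture precedes dosing and cannot date an event in a period counted from the dose.

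**7. Day 22.** The only timing data in the protocol (3.2.1) are a median time to ventilator-associated pneumonia of 10 days, range 3 to 16, from one clinical report. The protocol does not say from what point that time was counted, so this is a rough guide, but it suggests few boundary cases.

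**8. Scale, as illustration only.** Take the planned rates, 20% on placebo and 10% on MEDI3902. If a fraction f of events were lost equally in both arms, the relative risk would be 0.10(1 − f) / 0.20(1 − f) = 0.5, unchanged. Power is Φ(ln 2 / SE − 1.2816), with SE² = [(1 − p1)/p1 + (1 − p2)/p2] / n. With 143 per arm and no loss, SE² = 13/143 and power is 84.6%. With f = 10%, the rates are 18% and 9%, SE² = 14.667/143 and power is 81.1%. The documents do not support any particular value of f.

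**The case for a change.** The strongest case for a change is that this is the primary endpoint, that both documents use the same word for what may be different time points, and that the SAP's example does not satisfy its own rule. The hedges give the EAC discretion without saying how to use it, and the adjudication charter is not among the documents. One sentence naming the anchor would need no new data.

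Much of this stands. The ambiguity is real, and the rule and the example are loosely matched. What does not stand is the step from ambiguity to lost events. It needs three things at once: the SAP date starts the culture clock, fever prompts no specimen within 24 hours, and the EAC applies the clock mechanically despite its stated discretion. The text requires none of them.

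The concrete alternative, dating onset when the full clinical criterion is met, is a trade-off. It would move onset later, by about a day for some events. It would need windows running both before and after the anchor, so that a specimen or X-ray taken at the first sign still counts. The protocol has adjudication running during the study and this SAP is version 3.0 of February 2020, so a new anchor could also mean re-dating cases already adjudicated.

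**Conclusion.** No change to the plan follows. The text leaves out a detail, namely which time point starts the 24- and 72-hour windows, and a blinded adjudication committee can be expected to fill it sensibly. Excluding colonisation cultures explicitly would only restate what the new-signs requirement and the culture window already imply.

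The size cannot be given as a share of trial events. In the SAP's own example the risk of missing the ventilated window is nil if a specimen is taken at the fever. It is 50% to 88% if the first specimen comes 0 to 12 hours after the secretions, assuming uniform clock times and a clock that starts at the fever. The 72-hour window is not at risk unless sampling lags the secretions by more than a day. Day 22 boundary cases are probably few.

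The conclusion rests on adjudication staying blinded, so that any misclassification does not favour an arm, and on sites sampling when infection is first suspected, as the protocol asks. The charter and the redacted SAP text could not be checked and may already settle the anchor.
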